The trial will be performed in **18 subjects** with mCRC with liver metastasis and the safety of immunotherapy (durvalumab) with Y90-RE will be investigated in an accelerated titration design. This would allow a maximum tolerated dose with the minimum number of subjects. At any point as noted below if there is a DLT, the study design defaults to a standard 3+3 design. Assuming a 10% loss of subjects after enrollment, the dose escalation design will require at least 9 evaluable subjects to establish the highest dose level as the maximum tolerated dose (MTD). If less than 18 subjects are administrated in the dose escalation, the rest of subjects will be administrated the MTD in the expansion cohort. **Sample size of maximum of 18 was based on an accelerated titration design and on the correlative studies including pre- and post-biopsies. The primary goal of this study is to establish safety and with a secondary goal of looking at biomarkers and other immune signals as noted.**

This study will utilize an accelerated titration design. The dose levels to which patients will be assigned in sequential cohorts are listed in the table 1.

Table 1. Dose escalation cohort of durvalumab*

		Immunotherapy (Durvalumab) Administrations						Number of Administration of Durvalumab	
Dose level	Pre-Y90 doses		Post-Y90 doses			Week2	Week4	Week6	
	Week-2	Week0	Week2	Week4	Week6				
-2					X				1
-1				X	X				2
1 (start)**	X	X							2
2	X	X		X					3
3	X	X		X	X				4
4	X	X	X	X	X				5

* Please note: As noted above, the rationale for the proposed dosing schema is keeping in mind the timing of toxicities that are typically seen post Y90-RE. Most patients have elevation of their liver enzymes the first 1-2 weeks. Therefore, with the dosing escalation, we did not include the added dose at week 2 for the first dose escalation (dose level 2). Patients get fixed dosing of immunotherapy, which is the case for all immunotherapy-based studies. Depending on the dose level, patients can get a maximum of 2 doses before and 3 doses post Y90-RE (dose level 4).

**While dose level 1 and dose level -1 have the same number of durvalumab administrations, they are different since dose level 1 get 2 doses pre-Y90-RE ('priming doses of immunotherapy before Y90-RE) while dose level -1 only get 2 doses post-Y90-RE.

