A single patient will be treated per dose level until the first DLT is recorded. Once the first DLT is recorded, two additional patients are treated at the same dose level and the trial reverts to a standard 3+3 design. At which time, decisions on when and how to dose escalate are described below.

Number of patients with DLT at a given dose level	Decision Rule
0 out of 3	Enter 3 patients at the next higher dose level
1 out of 3	Enter up to 3 additional patients at the same dose level. 
 • If 0 of these 3 patients experience DLT, proceed to the next dose level. • If 1 or more of these 3 patients experience DLT, then dose escalation is stopped, and this dose is declared the maximally administered dose. Three (3) additional patients will be entered at the next lowest dose level if only 3 patients were treated previously at that dose.
≥ 2 out of 3	Dose escalation will be stopped. This dose level will be declared the maximally administered dose. Three (3) additional patients will be entered at the next lowest dose level if only 3 patients were treated previously at that dose.

Up to 6 patients will be treated at each dose level. The MTD will be defined as the highest dose level for which at most 1 out of 6 patients experience a DLT. If DLT meets the stopping boundaries set by the above dose algorithm at dose level 1 (for example, more than 1 out of 3 or more than 1 out of 6 patients), the next cohort of 3 patients will be entered at the dose level of -1. If dose level -1 meets the stopping boundaries, the next cohort of 3 patients will be entered at dose level -2.

If an MTD is determined, an expansion cohort using the RP2D will be carried out in additional patients for a maximum of 18 patients. If an MTD is not determined, the expansion cohort will utilize the dosing scheme from cohort 4.

After the end of treatment visit (EoT) subjects (if applicable) are to resume the previously discontinued chemotherapy until all cycles have been administered or treatment is discontinued as per regular standard of care or secondary resection if deemed a candidate. The decision to resume the previously discontinued chemotherapy is to be done at investigators discretion. As the patients will commence a different treatment regime, no active follow-up will be done as part of this study other than progression free survival and overall survival.

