7. Gross (dipstick) urine examination: Leukocytes, nitrite, pH, protein, glucose, ketone, urobilinogen, bilirubin, blood (hemoglobin and erythrocytes). If abnormalities are detected by dipstick, then a microscopic sediment test should also be performed. If a UTI is suspected, it can be treated.
8. Durvalumab administration over 60 minutes. Following infusion, subjects must be observed for 30 minutes post infusion for potential infusion related reactions. The number of doses administered is per dose level for each patient cohort.
9. The 2nd durvalumab dose can be done \leq 5 days prior to Y90-RE or same day as long as it is before the Y90-RE.
10. Blood biomarkers will be collected in the morning of visit. Kits are required.
11. Tissue specimens must be collected the following timepoints: pre-treatment [screening/prior to cycle 1 of Durvalumab (fresh as well as archived if available)], and post-treatment. Kits are required (banking, clinical as well as real-time send out).
12. Visit will occur 8 weeks after Y90-RE.
13. Clinical follow-up visits will be performed at least every 3 months (or as per standard physician practice) for 2 years.
14. Cohort 1- Durvalumab given at cycle 1 and cycle 2 only
15. Cohort 2- Durvalumab given at cycle 1, 2, and 4
16. Dose escalation cohort- Durvalumab given cycle 1, 2, 4 and 5
17. Dose expansion cohort- Durvalumab given cycle 1, 2, 3, 4, and 5
18. As long as the lesion is amenable to a biopsy and is done, the biopsy can be done on the Tc-99m labelled MAA eligibility mapping day to save patient a visit. Has to be prior to anti-PD1 therapy though. From a safety perspective since we need to know about the shunting to other organs prior to the Y90-RE, the mapping can be done during the screening or even prior to considerations for this study if already performed within 12 months of intended Y90-RE, it would not need to be repeated unless as per interventional radiology. Biopsy still needs to be done as noted.
19. If there is complete response of the lesion in the field of Y90-RE, tissue biopsy of the field would still be done to assess for the immune changes and an alternative tumor lesion can be biopsied for testing of the tumor itself.
20. At the time of progression, patient would be approached for a tissue biopsy and research blood sampling similar to the end of treatment visit.

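### Footnote 17 of the test schedule gives the expansion cohort the five-dose level 4 schedule without condition, which contradicts the MTD/RP2D expansion rule if the declared MTD is below level 4

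*Combined protocol and SAP*

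**What the plan says.** Section 4.1 attaches cohort schedules to the test-schedule table in footnotes 14 to 17. Footnote 14 gives cohort 1 cycles 1 and 2. Footnote 15 reads "Cohort 2- Durvalumab given at cycle 1, 2, and 4", footnote 16 "Dose escalation cohort- Durvalumab given cycle 1, 2, 4 and 5" and footnote 17 "Dose expansion cohort- Durvalumab given cycle 1, 2, 3, 4, and 5". Footnote 8, on the durvalumab row, adds a general statement: "The number of doses administered is per dose level for each patient cohort".

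Section 1.4.6 sets a conditional rule for expansion. With an MTD: "If an MTD is determined, an expansion cohort using the RP2D will be carried out in additional patients", up to 18 patients in total. Without one: "If an MTD is not determined, the expansion cohort will utilize the dosing scheme from cohort 4". An earlier paragraph of 1.4.6, and section 1.4.7, also place the remaining patients at the MTD. The MTD is the highest level at which no more than 1 of 6 patients has a DLT (sections 1.4.6 and 17.2), so it can lie below level 4. De-escalation is provided for too: if level 1 fails, "the next cohort of 3 patients will be entered at the dose level of -1".

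**The concern.** The four footnotes reproduce dose levels 1 to 4 in order, but the labels change halfway. The first two are called cohorts 1 and 2, the third the escalation cohort and the fourth the expansion cohort. All four are escalation levels. The level 4 schedule therefore appears in section 4.1 only under the name of the expansion cohort, and footnote 17 is the only line there that names that cohort.

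Read on its own, it is a fixed instruction: expansion patients receive five infusions whatever escalation showed. If level 4 had been rejected for toxicity, that is the rejected schedule. If escalation had stopped before level 4, it is a schedule no patient had received. Table 1 withholds the week 2 dose until level 4. Section 1.4.5 explains that this dose was left out of the first escalation because liver enzymes usually rise in the first one to two weeks after Y90-RE. In a first trial of this combination, a dosing line that bypasses the escalation result should not stand.

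**Working it through.** **Plan's own figure.** Section 17.3 expects 9 evaluable patients to establish the highest level as the MTD. One patient at each of levels 1 to 3 plus six at level 4 gives 1 + 1 + 1 + 6 = 9, so the figure is reproduced. That leaves 18 - 9 = 9 expansion patients, who receive the level 4 schedule under either text.

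**Inputs.** Schedules and dose totals come from Table 1 (section 1.4.6). A cycle is 14 days and cycle 2 carries Y90-RE (section 4.1), so weeks -2, 0, 2, 4 and 6 are cycles 1 to 5. Each dose is 750 mg (section 7.1.1).

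**Formula.** Extra infusions per expansion patient = 5 (footnote 17) minus the number of doses at the declared MTD level.

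| Declared MTD | Cycles due under 1.4.6 | Doses due | Extra under footnote 17 | Extra cycles |
|---|---|---|---|---|
| Level 4, or no MTD | 1-5 | 5 | 5 - 5 = 0 | none |
| Level 3 | 1, 2, 4, 5 | 4 | 5 - 4 = 1 | 3 |
| Level 2 | 1, 2, 4 | 3 | 5 - 3 = 2 | 3, 5 |
| Level 1 | 1, 2 | 2 | 5 - 2 = 3 | 3, 4, 5 |
| Level -1 | 4, 5 | 2 | 5 - 2 = 3 | 1, 2, 3 |
| Level -2 | 5 | 1 | 5 - 1 = 4 | 1, 2, 3, 4 |

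In drug terms the excess runs from 1 × 750 = 750 mg to 4 × 750 = 3,000 mg per patient. At an MTD of level 3 the single extra dose is cycle 3 (week 2), the one dose that separates level 3 from level 4. At level -1 the excess includes both doses before Y90-RE, whereas Table 1's note says "dose level -1 only get 2 doses post-Y90-RE".

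**How many patients.** The documents do not fix this. One path as an example: no DLT in the single patients at levels 1 and 2, level 4 rejected after 3 to 6 patients, and level 3 filled to six. Escalation uses 1 + 1 + 6 + 3 = 11 to 1 + 1 + 6 + 6 = 14 patients, leaving 18 - 11 = 7 down to 18 - 14 = 4 for expansion. As an illustration only, simulating the escalation rule with assumed flat DLT rates of 5% to 20%, and filling the MTD level to six, left an average of about 5 expansion patients when the MTD fell at levels 1 to 3. The documents give no DLT rates.

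**The case against.** The best reply is that footnote 17 is the level 4 line under the wrong name, and that other text already governs dosing. Footnote 8 ties the number of doses to dose level. Section 7.1.1 sends staff to Table 1 for number and timing. Sections 1.4.2 and 3.0 require the dose level to be obtained from the investigator or coordinator, at a single site. Section 17.3 does not expect DLTs, and on that path nothing conflicts.

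Most of this stands, and it is why the point is minor. It does not remove the contradiction. Footnote 8 does not mention expansion, MTD or RP2D. Section 7.1.1 speaks of the cohort assigned during escalation and gives the wrong section number for Table 1 (1.23; the table is in 1.4.6). Table 1 has no expansion row.

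Three stronger readings are tempting and not supported:

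- **That expansion patients would be overdosed, or that the design ignores the MTD.** The design sections state the rule correctly, and the assignment steps make a wrong dose unlikely.
- **That about 7 or 10 patients would be affected.** Such averages arise if the backfill rule is read as adding three patients, or as adding three only where exactly three had been treated. In most such trials the supposed MTD rests on fewer than six patients. That does not meet the 1-in-6 definition or section 17.2's six patients at the MTD. Read literally, no MTD is then determined and 1.4.6 gives the cohort 4 scheme, as footnote 17 does.
- **That the schedule is deficient because no footnote covers levels -1 and -2.** Table 1 sets them out and footnote 8 refers to dose level.

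**Conclusion.** The point holds as a minor error in the wording of the test schedule. For any declared MTD below level 4, footnote 17 and the expansion rule of sections 1.4.6 and 1.4.7 prescribe different schedules. The difference is 1 to 4 infusions per expansion patient, always in the direction of more drug. It is zero if level 4 is the MTD or no MTD is determined.

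The dose differences come directly from Table 1. They assume that RP2D and MTD denote the same dose level, as sections 1.4.6 and 1.4.7 appear to use them. The patient counts above are not findings: they depend on assumed DLT rates and on how the MTD level is filled.

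The superscripts on the durvalumab row are a separate clerical matter. They run two higher than those on the research-specimen row in the same pattern, so cycle 3 dosing cites only note 19, a biopsy note. This may be a fault of text extraction, and the conclusion does not rest on it.

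**What to change.** Relabel footnote 16 as *Cohort 3 (dose level 3)* and footnote 17 as *Cohort 4 (dose level 4)*, keeping their cycles. Add one line: *Expansion cohort: durvalumab per the declared MTD/RP2D dose level (Table 1); dose level 4 schedule only if no MTD is determined.*

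In the same pass, check the superscripts on both the durvalumab and research-specimen rows against the published table. On the research-specimen row, cycle 5 cites note 15, although that note doses cohort 2 at cycles 1, 2 and 4 only.

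The cost is a wording amendment. No patients, visits or escalation rules change.

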4.0 Test Schedule

4.1 Test schedule for metastatic CRC

Tests and procedures	Screening		Active Monitoring Phase					
	Reg	Cycle 1	Cycle 2 (2 nd dose of Durva + Y90-RE)*	Cycle 3	Cycle 4	Cycle 5	End of treatment visit ¹²	Clinical Follow-up ¹³ (every 3 months)
Window	21 days	±5 days	±5 days	±5 days	±5 days	±5 days	±5 days	
History and exam ³ , Wt ⁵ , BP, HR, ECOG PS	X							
Exam, Wt ⁵ , BP, HR, ECOG PS		X	X	X	X	X	X	X
Adverse event assessment	X	X	X	X	X	X	X	X
Concomitant medication review	X	X	X	X	X	X	X	X
Height	X							
IR Consult	X							
Pregnancy test ¹	X		X		X		X	X
Hematology group CBC w/ 5-part differential	X	X	X	X	X	X	X	X
Chemistries ²¹	X	X	X	X	X	X	X	X
Thyroid Function Test TSH, free T4, amylase, lipase, Vitamin D	X		X		X		X	X
Creatinine clearance	X	X	X	X	X	X	X	X
Coagulation PT, PTT, INR	X						X	
Cholesterol, triglycerides	X							
IR Tc-99m labelled MAA eligibility mapping		X ¹⁸						
Tumor measurement ²	X						X	X
ECG ⁶	X		X		X		X	
Urinalysis ⁷	X	X	X	X	X	X	X	X
Administer durvalumab ^{8,R}		X ^{16,17,18,19}	X ^{9,16,17,18,19}	X ¹⁹	X ^{17,18,19}	X ^{17,18,19}		
Administer Y90-RE			X					
Patient Questionnaire Booklets ⁴ (Appendix III)		X	X	X	X	X	X	
Mandatory Research Specimens (see companion Lab Manual) ^{10,R}	X	X ^{14,15,16,17}	X ^{14,15,16,17}	X ¹⁷	X ^{15,16,17}	X ^{15,16,17}	X	
Mandatory Research Tissue specimens (see companion Lab Manual) 11,R	X (Pre- treatment) ₁₈						X (Post- treatment) _{19, 20}	

Cycle = 14 days

1. For women of childbearing potential only. Serum pregnancy test. Must be done \leq 7 days prior to registration.
2. A scan is required at baseline prior to the first dose of durvalumab. The scan does not need to be repeated as long as it is \leq 28 days prior to registration. Preferably we would recommend a CT of the chest and pelvis; and an MRI of the abdomen for assessment of liver metastases. If an MRI cannot be performed, a CT chest, abdomen, and pelvis would be acceptable. Please use same imaging throughout the study.
3. History and exam include prior surgery, cancer-related and other treatment and known positivity for Hepatitis B surface antigen, Hepatitis C virus antibodies, and Human Immunodeficiency Virus antibodies 1 /-2.
4. Patient questionnaire booklets **must** be used; copies are not acceptable for this submission
5. Body weight to be measured within 72 hours prior to durvalumab administration.
6. Single 12-lead ECG after 5 min rest in supine position.

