21. Creatinine, ALP, ALT, AST, total bili, direct bilirubin, AlkPhos, GGT, total protein, uric acid, BUN, Na, K, Ca, Cl, LDH, CPK, inorganic phosphate, CEA, CA-19-9, ESR, CRP

* 2 research blood drawn (pre-post Y90 RE on the day of procedure). Timing not important.

R Research funded (see Section 19.0)

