7.4.2 Definitions of Dose Limiting Toxicities (DLT)

A DLT will be defined as any Grade 3 or higher treatment-related toxicity that occurs during the DLT observation phase (8 weeks post Y90-RE), including:

- Any event resulting in a delay of cycle 2 by \geq 14 calendar days
- Any Grade 4 immune related adverse event (irAE)
- Any Grade 3 immune related AE (irAE) that does not resolve to \leq Grade 1 or to baseline with immunosuppressive therapy within 3 weeks
- Any Grade 3 colitis
- Any Grade 3 noninfectious pneumonitis irrespective of duration
- Grade 4 neutrophil count decreased lasting longer than 5 calendar days
- Grade 4 platelet count decreased
- Grade 3 platelet count decreased with hemorrhage
- Any \geq Grade 2 pneumonitis that does not resolve to \leq Grade 1 within 7 days of the initiation of maximal supportive care
- Any other Grade 3 irAE (excluding colitis or pneumonitis), that does not downgrade to Grade 2 within 7 days after onset of the event despite optimal medical management including systemic corticosteroids or does not downgrade to \leq Grade 1 or baseline within 14 days
- Liver transaminase elevation $> 8 \times$ ULN
- Total bilirubin $> 5 \times$ ULN
- AST or ALT $> 5-8 \times$ ULN with concurrent increase in total bilirubin $> 2 \times$ ULN without evidence of cholestasis or alternative explanations, e.g., viral hepatitis, disease progression in the liver, etc. (Hyll's Law). Exception: If it is present at cycle 3 but resolves at cycle 4 it is not a DLT.
- Any \geq grade 3 non-hematologic toxicity, except:
 - Grade 3 nausea or vomiting that lasts < 48 hours and resolves to \leq Grade 1 either spontaneously or with conventional medical intervention
 - Grade 3 nausea, vomiting, and diarrhea lasting < 72 hours in the absence of maximal medical therapy
 - Grade 4 vomiting and diarrhea lasting < 72 hours in the absence of maximal medical therapy
 - Grade 3 hypertension in the absence of maximal medical therapy
 - Grade 3 metabolic abnormalities (e.g. hypokalemia, hypomagnesemia, hypocalcemia, hypophosphatemia) that recover to \leq Grade 1 within 48 hours
 - \geq Grade 3 electrolyte abnormality lasting < 72 hours, is not clinically complicated, and resolves spontaneously or responds to conventional medical intervention.
 - Grade 3 or 4 elevation in serum amylase and/or lipase that are not associated with clinical or radiographic evidence of pancreatitis.
 - Grade 3 rash < 5 calendar days

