8.2 Treatment schedule modifications for durvalumab

Adverse events (both non-serious and serious) associated with durvalumab exposure may represent an immunologic etiology. These adverse events may occur shortly after the first dose or several months after the last dose of treatment. Durvalumab must be withheld for drug-related toxicities and severe or life-threatening AEs per Table 8.21 below. See Section 9.0 for supportive care guidelines, including use of corticosteroids.

Table 8.21 Dose Modification Guidelines for Drug-Related Adverse Events for Durvalumab			
CTCAE System/Organ/Class	Adverse Event	Grade	Action
Gastrointestinal disorders	Diarrhea or Colitis	2	Hold all protocol treatment until Grade 0-1. If AE does not resolve to Grade 0-1 within 2 weeks, then permanently discontinue all protocol treatment
		3, 4	Permanently discontinue all protocol treatment
Investigations	Alanine aminotransferase increased, Aspartate aminotransferase increased, and blood bilirubin increased	2	Hold all protocol treatment until Grade 0-1. If AE does not resolve to Grade 0-1 within 2 weeks, then permanently discontinue all protocol treatment
		3-4	Permanently discontinue all protocol treatment
Metabolism and nutrition disorders	Glucose intolerance (Type 1 diabetes mellitus [if new onset]) or Hyperglycemia	T1DM or 2-4	Hold all protocol treatment until clinically and metabolically stable.

Table 8.21 Dose Modification Guidelines for Drug-Related Adverse Events for Durvalumab

CTCAE System/Organ/Class	Adverse Event	Grade	Action	
Endocrine disorders	Endocrine disorders-Other, specify: Hypophysitis	2-4	Hold all protocol treatment until Grade 0-1. If AE does not resolve to Grade 0-1 within 2 weeks, then permanently discontinue all protocol treatment	
	Hypothyroidism	2-4	Therapy with durvalumab can be continued while thyroid replacement therapy is instituted	
	Hyperthyroidism	2-3	Hold all protocol treatment until Grade 0-1. If AE does not resolve to Grade 0-1 within 2 weeks, then permanently discontinue all protocol treatment	
		4	Permanently discontinue all protocol treatment	
General disorders and administration site conditions	Infusion related reaction	1, 2	Follow infusion related reaction treatment guidelines (Table 9.21). Hold all protocol treatment until Grade 0-1. If AE does not resolve to Grade 0-1 within 2 weeks, then permanently discontinue all protocol treatment	

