- whose Tc-99m macroaggregated albumin (MAA) hepatic arterial perfusion scintigraphy shows any deposition to the gastrointestinal tract that may not be corrected by angiographic techniques (see Item 1 under **INDIVIDUALIZATION OF TREATMENT**);
- who show shunting of blood to the lungs that could result in delivery of greater than 16.5 mCi of yttrium-90 to the lungs. Radiation pneumonitis has been seen in patients receiving doses to the lungs greater than 30 Gy in a single treatment (see Item 2 under **INDIVIDUALIZATION OF TREATMENT**);
- in whom hepatic artery catheterization is contraindicated; such as patients with vascular abnormalities or bleeding diathesis;
- who have severe liver dysfunction or pulmonary insufficiency; and
- who present with complete occlusion of the main portal vein (see Item 3 under **INDIVIDUALIZATION OF TREATMENT**).

PRECAUTIONS/WARNINGS

A retrospective study of 121 patients from 5 clinical trials has shown that the following 5 Pre-treatment High Risk Factors have been associated with at least 48% of all serious adverse events that were possibly related to use of the device and with 11 of the 12 deaths that were possibly related to use of the device:

- infiltrative tumor type
- "Bulk disease" (tumor volume > 70% of the target liver volume, or tumor nodules too numerous to count)
- AST or ALT > 5 times ULN
- bilirubin > 2 mg/dL
- tumor volume > 50% combined with an albumin < 3 g/dL

The physician should always take the above-noted Pre-treatment High Risk Factors into consideration for each patient when making decisions regarding the use of TheraSphere® for treatment.

- Radioactive products should be used only by physicians who are qualified by specific training in the safe use and handling of radionuclides and whose experience and training have been approved by the appropriate government agency authorized to license the use of radionuclides.
- Adequate shielding and precautions for handling radioactive material must be maintained.
- As in the use of any radioactive material, care should be taken to ensure minimum radiation exposure to the patient extraneous to the therapeutic objective and to ensure minimum radiation exposure to workers and others in contact with the patient.

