AChE Acetylcholine esterase; ADL Activities of daily living; AE Adverse event; ALP Alkaline phosphatase test; ALT Alanine aminotransferase; AST Aspartate aminotransferase; BUN Blood urea nitrogen; CT Computed tomography; CTCAE Common Terminology Criteria for Adverse Events; ILD Interstitial lung disease; imAE immune-mediated adverse event; IG Immunoglobulin; IV Intravenous; GI Gastrointestinal; LFT Liver function tests; LLN Lower limit of normal; MRI Magnetic resonance imaging; NCI National Cancer Institute; NCCN National Comprehensive Cancer Network; PJP *Pneumocystis jirovecii* pneumonia (formerly known as *Pneumocystis carinii* pneumonia); PO By mouth; T3 Triiodothyronine; T4 Thyroxine; TB Total bilirubin; TNF Tumor necrosis factor; TSH Thyroid-stimulating hormone; ULN Upper limit of normal.

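### The scheduled chemistry panel lists alkaline phosphatase twice but omits serum glucose, magnesium and albumin, so a hold rule, part of the DLT definition and a device precaution lack planned measurements

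*Combined protocol and SAP*

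**What the plan says.** Table 4.1 marks Chemistries at registration, at cycles 1 to 5, at the end-of-treatment visit and at clinical follow-up. Footnote 21 gives the content: "Creatinine, ALP, ALT, AST, total bili, direct bilirubin, AlkPhos, GGT, total protein, uric acid, BUN, Na, K, Ca, Cl, LDH, CPK, inorganic phosphate", then CEA, CA-19-9, ESR and CRP. The abbreviation list that closes the toxicity tables in Appendix VII gives "ALP Alkaline phosphatase test", so ALP and AlkPhos are one test.

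The nearest other blood row is "Thyroid Function Test TSH, free T4, amylase, lipase, Vitamin D". The remaining laboratory rows are CBC with differential, creatinine clearance, coagulation, lipids (screening only), a pregnancy test and urinalysis. Footnote 7 describes the last as "Gross (dipstick) urine examination: Leukocytes, nitrite, pH, protein, glucose, ketone" and further dipstick items.

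Three parts of the protocol use the missing values:

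- Table 8.21 has a row for "Glucose intolerance (Type 1 diabetes mellitus [if new onset]) or Hyperglycemia". It holds all protocol treatment for T1DM or Grades 2 to 4.
- Section 7.4.2 makes any related Grade 3 or higher non-hematologic toxicity a DLT, subject to exceptions. One exception covers "Grade 3 metabolic abnormalities (e.g. hypokalemia, hypomagnesemia, hypocalcemia, hypophosphatemia") if they recover to Grade 1 or less within 48 hours.
- Section 16.1.6 plans and gives the device according to its package insert. Under Precautions/Warnings (Appendix VI), the insert lists five pre-treatment high-risk factors that the physician should always consider. One is "tumor volume > 50% combined with an albumin < 3 g/dL".

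**The concern.** A rule that turns on a laboratory value works as intended only if someone is bound to measure that value. Here the schedule can be followed to the letter without producing a serum glucose, a magnesium or an albumin at any visit, including baseline.

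The primary goal (Section 2.1) is feasibility and safety. In the accelerated phase each dose level rests on one patient until the first DLT, which switches the trial to 3+3. A toxicity that is not measured can only lower the recorded count. If clinicians order these tests for some patients and not others, ascertainment will also differ between patients and dose levels for reasons unrelated to treatment. Without a screening value, a low albumin or magnesium found later cannot be separated from a pre-existing one, which weakens attribution.

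**Working it through.** The plan gives no figure on this point to reproduce. The check sets the schedule beside the rules, then illustrates the size.

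**Step 1: count the panel.** Footnote 21 has 22 entries. Merging ALP with AlkPhos leaves 22 − 1 = 21 distinct analytes. Glucose, magnesium and albumin: 0 of 3 present. Total protein is listed but is not albumin.

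**Step 2: match the rules to scheduled tests.**

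| Rule | Value needed | Scheduled? |
|---|---|---|
| Table 8.21, T1DM or hyperglycemia Grade 2-4 | glucose | urine dipstick only |
| 7.4.2, 48-hour metabolic exception | potassium, calcium, phosphate | yes |
| 7.4.2, same exception | magnesium | no |
| 7.4.2, Grade 3+ non-hematologic catch-all, if related hypoalbuminemia | albumin | no |
| Insert risk factors: AST/ALT; bilirubin | AST, ALT, bilirubin | yes |
| Insert risk factor: tumor volume with albumin | albumin | no |

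Three of the four metabolic examples in 7.4.2 are covered; magnesium alone is not. Three of the five insert risk factors involve a laboratory value; only the one using albumin lacks its test.

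**Step 3: look for the values elsewhere.** Section 9.5.3 asks for serum glucose once T1DM or Grade 3-4 hyperglycemia is present. Appendix VII mentions blood glucose when an endocrinopathy is suspected. Both are work-up, not surveillance, and the first starts above the Grade 2 at which Table 8.21 acts. The companion laboratory manual, which is not among the documents, is cited for research specimens rather than safety chemistry.

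**Step 4: illustrate the size for albumin**, the only one of the three for which the documents give a usable rate.

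- Insert Table 2 (Appendix VI): Grade 3 or higher decreased albumin in 57 of 411 patients from 3 studies; p = 57/411 = 0.1387. Within-study range 0.0% to 33.3%.
- Chance of at least one event in n patients: 1 − (1 − p)^n.
- Single-patient phase, at most n = 4 (levels 1 to 4, one evaluable patient each): 1 − 0.8613^4 = 0.45. At 0.0% this is 0; at 33.3% it is 1 − 0.667^4 = 0.80.
- Full accrual, n = 18: 1 − 0.8613^18 = 0.93. At 0.0% this is 0; at 33.3% it is 1 − 0.667^18 = 0.999.
- Expected events in 18: 18 × 0.1387 = 2.5, with a range of 0 to 18 × 0.333 = 6.0.

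These are chances that an event occurs, not that a DLT is missed. A DLT must also be treatment-related, fall within 8 weeks after Y90-RE and meet no exception.

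**The case against.** The best case against this point is that the schedule sets a minimum. Nothing bars further tests; adverse events are assessed at every visit; Section 1.4.2 describes two-weekly visits with labs after Y90-RE as preferred standard practice; and a value obtained in routine care can be graded and reported. Because Section 16.1.6 adopts the insert, and an interventional radiology consult and suitability review are required, an albumin check is already called for by reference. This stands to the extent that a reader might infer these toxicities cannot be detected at all, or that the albumin factor cannot be checked. The documents support neither. They support only that the schedule does not guarantee the values.

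Other tempting readings also go too far:

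- *Hypomagnesemia as a named DLT trigger.* It is an example inside an exception to the Grade 3 or higher catch-all. Even with magnesium on a 14-day panel, a 48-hour recovery would need a repeat test, as it does for potassium, calcium and phosphate.
- *Glucose as wholly unmeasured.* Urine glucose and ketone are scheduled at each visit. The documents do not reproduce the CTCAE v5.0 grade definitions, so I do not argue from them what a Grade 2 call requires.
- *Albumin as an eligibility limit.* Section 3.2 contains none; the insert's factor is a precaution to consider.
- *93% as the chance of a missed DLT.* It uses all 18 patients, including the expansion cohort, and a rate from HCC patients. The insert describes grading in that review under CTCAE 2.0 and 3.0, while this trial uses 5.0, and the table states no time window.

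What the objection does not answer is that reliance on unplanned tests leaves ascertainment to individual habit in a trial that decides on very few patients.

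**Conclusion.** The mismatch is real and should be corrected. Alkaline phosphatase is listed twice; serum glucose, magnesium and albumin are not scheduled anywhere; and each is used by a rule or precaution the protocol relies on. The consequence is possible under-recording and uneven ascertainment of laboratory toxicity, not a certainty that events are missed.

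The omission follows directly from the text. The magnitude does not: the figures of 45% (0% to 80%) in four patients and 93% (0% to over 99%) in 18 assume that a rate from HCC patients, graded under older criteria, carries over and that patients are independent. Only some such events would count as DLTs. The documents give no comparable rate for magnesium or glucose, so none is offered. The point does not depend on these figures.

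**What to change.** Reconcile footnote 21 with Section 7.4.2, Table 8.21 and the insert precaution. Remove the duplicate alkaline phosphatase entry and add serum glucose, magnesium and albumin to the panel already drawn at screening and through the end-of-treatment visit. Footnote 12 places that visit 8 weeks after Y90-RE, so this covers the DLT window and gives a baseline. The hold, DLT and device rules stay as they are. The sponsor should confirm what the second alkaline phosphatase entry was meant to be; the documents do not show that it stood for any of the three.

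The cost is one footnote edit and three analytes on blood already being drawn. The downside is that a few more laboratory adverse events, and possibly DLTs, will be recorded.
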